#### 9.3.4. Exploratory Endpoints

All exploratory endpoints will be summarized on the ITT population.

- Levels of uricase activity in patients receiving SEL-212:

Summaries for each SEL-212 treatment group will be provided by period.

- Effect on monosodium urate crystal deposits and/or total body monosodium urate crystal deposits (imaging patients only):

Frequencies and summaries will be provided by treatment group, and period, if appropriate.

- Levels of inflammatory and tolerogenic biomarkers:

Frequencies and summaries will be provided by treatment group, and period, if appropriate..

- Changes in antibody production (anti-uricase and anti-pegadricase) in patients in the SEL-212 groups:

Summaries for each SEL-212 treatment group will be provided by period.

- Gout flare incidence during Treatment Periods 4-6

A summary table of incidence of gout flares during TPs 4-6 will be presented, based on the ITT population, but including only patients who were still being followed up at the start of TP 4. The incidence is defined as the total number of gout flares a patient experiences between TP4 day 0 and TP6 day 28, divided by the length of observation of the patient in this time period.

An ANCOVA model will be performed with incidence of gout flares as the dependent variable, and treatment and randomization stratum as fixed effect variables. The LSMean difference between

This document is confidential.

**Statistical Analysis Plan**

Sponsor: Selecta Biosciences

Protocol No.: SEL-212/302

each SEL-212 and placebo treatment group will be provided along with its 95% confidence interval, and 2-sided p-values.

- Gout flare incidence based on self-reported weekly gout flare diary:

A summary table of the incidence of gout flares during the study and during the first 3 months and the next 3 months after start of study treatment based on weekly gout flare diary will be provided by treatment group on the ITT population. The incidence is defined as the total number of gout flares a patients experiences in respective time period divided by the length of observation of the patient in this time period. Additionally a summary table of the total number of gout flares during the study, and of the total number of gout flares during the first 3 months and the next 3 months after start of study treatment will be provided by treatment group and severity on the ITT population.

An ANCOVA model will be performed with incidence of gout flares as dependent variable and treatment and randomization stratum as fixed effect variables for the whole treatment period (TP1 to 6) and for the first 3 months (TP1 to 3) on the ITT. The LSMean difference between each SEL-212 and placebo treatment group will be provided along with its 95% confidence interval, and 2-sided p-values.

Additionally, a MMRM will be applied on the ITT with the dependent variable 'incidence of gout flares in the study (TP1-6)' and treatment, 3-month period (months 1-3 versus months 4-6), treatment-by-3-month period interaction, randomization stratum and baseline value of number of gout flares as fixed effects. The LSMean difference between each SEL-212 and placebo treatment group will be presented for each 3-month period, along with its 95% confidence interval, and 2-sided p-values.

- Association between multiomic markers of gout and treatment effect in patients treated with SEL-212

The treatment effect at TP6, i.e., the number and percentage of patients with responses as defined for the primary efficacy variable (i.e. having sUA value < 6 mg/dL in more than 80% of the time in TP6) will be summarized for each class of multiomic markers by SEL-212 treatment group.

- Immune tolerance related multiomic markers in patients on SEL-212 who developed anti-uricase vs. those patients on SEL-212 that did not develop anti-uricase antibodies, and in patients on SEL-212 who developed anti-pegadricase antibodies vs. those patients on SEL-212 that did not develop anti-pegadricase antibodies:

Summaries for each SEL-212 treatment group will be provided by period and by antibody status.

This document is confidential.

## 10. Safety

The population used for safety analyses will be the Safety Set (SS). All safety assessments will be listed by treatment group and patient ID. Visit-wise assessed safety parameters will be listed by treatment group, patient ID and visit/ timepoint. Unscheduled assessments will be flagged and presented in listings. Adverse events will be listed by treatment group, patient ID, start date/time and stop date/time.

### 10.1. Extent of Exposure

Number and percentage of patients who received all 6 cycles of study treatment (i.e., completed study treatment) and who received only 5, 4, 3, 2, or 1 cycles will be presented by treatment group and overall. The dose applied in each treatment period will be summarised by treatment group and overall SEL-212.

Number and percentage of patients who met the stopping rules will be summarized by treatment group, overall SEL-212 and treatment period. The percentage will be plotted versus treatment period by treatment group.

### 10.2. Treatment Compliance

Treatment compliance will be calculated for the two active components SEL-110.36 and SEL-037 for each SEL-212 treatment group separately in a first step. In a second step these compliances will be pooled to one overall compliance for each SEL-212 treatment group.

For each component SEL-110.36 and SEL-037 the following will be calculated for each patient in each of the SEL-212 treatment groups:

- 1) For each treatment period i and patient j: Compliance of SEL-xx in period i =  $100\% \times (\text{total volume infused in period i}) / (\text{total volume planned in period i})$ .
- 2) For each treatment period i and patient j: Overall compliance in period i =  $(\text{compliance of SEL-110.36 in period i} + \text{compliance of SEL-037}) / 2$ ;
- 3) Mean overall treatment compliance of patient j = Sum of overall compliances in all applied treatment periods of patient j divided by the number of applied treatment periods.

The overall treatment compliance for each period and the mean overall treatment compliance will be summarized and presented by SEL-212 treatment group.

Additionally the volume and infusion duration (defined as stop time of infusion – start time of infusion) in each treatment period will be summarized for each SEL-212 treatment group and for placebo.

### 10.3. Adverse Events / Adverse Drug Reactions

All adverse events (AEs) will be coded using the most recent MedDRA Version. All AEs will be summarized by system organ class (SOC) and preferred term (PT) for each treatment group, for overall SEL-212 and in total. A treatment-emergent AE (TEAE) is an AE that starts or worsens at any time after initiation of study drug on Day 0 of Treatment Period 1 until the End of Study Visit (30 days after completion of the last dose of study drug).

Following AEs are considered as AESI: gout flares, infections, malignancies, viral infections, interstitial lung disease, stomatitis, infusion-related reactions including anaphylaxis, thrombosis (e.g., deep venous thrombosis, pulmonary embolism), and the following laboratory tests, if deemed clinically significant by the PI: hyperlipidemia, worsening of renal function tests, proteinuria, and leukopenia.

This document is confidential.

**Statistical Analysis Plan**  
 Sponsor: Selecta Biosciences  
 Protocol No.: SEL-212/302

---

An overall summary will be provided of the number and percentage of patients reporting AEs, TEAEs, treatment-related (possibly related and related) TEAEs, serious TEAEs, treatment-related serious TEAEs, AEs of special interest (AESIs), infusion reactions (this is a study drug-related AE that occurs within 24 hours after initiation of study drug infusion), TEAEs leading to study drug withdrawal and TEAEs leading to death. In the overall summary, additionally, the number and percentage of patients with at least one severe TEAE, with at least one moderate TEAE but no severe TEAE and with only mild TEAEs will be provided. Additional analysis will be performed on a subset of infusion reactions (this is a study drug-related AE that occurs within 1 hour after completion of study drug infusion) that fulfil the criteria of an Allergic Reaction/Hypersensitivity according to the Rheumatology Common Toxicity Criteria, version 2.0. Any gout flare which occurs within 24 hours after initiation of study drug infusion will be listed as a gout flare and not as an infusion reaction.

The number and percentage of patients with TEAEs / treatment-related TEAEs / serious TEAEs / AESIs / TEAEs leading to study drug withdrawal/ will be summarized by SOC and PT for each treatment group, overall SEL-212 and total. TEAEs will also be summarized by SOC and PT for maximum intensity and maximum causality for each treatment group, overall SEL-212 and total.

Exposure-adjusted event rates based on i) patients and also based on ii) events by treatment group, overall SEL-212 and total will be provided for patients with at least one related TEAE, at least one SAE, at least one TEAE of special interest and also for specific TEAEs of special interest. For SAEs and AESIs that occur in  $\geq 2\%$  of individuals, as well as the most common TEAEs, the rate difference of exposure-adjusted event rates between the two treatment groups together with the 95% confidence interval will be provided; this will also be presented for the two treatment groups combined vs. placebo.

i) Exposure –adjusted event rate in treatment group A based on patients = Number of all patients with at least one event in treatment group A / Total sum of the treatment exposure time of all patients in treatment group A.

ii) Exposure –adjusted event rate in treatment group A based on events = Number of all events in treatment group A / Total sum of the treatment exposure time of all patients in treatment group A.

Listings of TEAEs and non-TEAEs will be provided.

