10.7 Administration

Before administration of study drug, patients will be premedicated with antihistamines and steroids as described in [Section 10.6](#). The timing of premedication and study drug administration are presented graphically in [Appendix C](#) and [Appendix D](#).

Patients will receive treatment with study drug on Day 0 of each treatment period for a total of 6 doses of study drug.

All study drugs should be administered through the same IV access. All blood samples should be drawn from an alternative venous access.

The reconstituted SEL-110.36 will be withdrawn from the vial and dosed via IV infusion with a syringe infusion pump utilizing an appropriately sized syringe. SEL-110.36 will be infused at a rate of 1.5 mL/hr for the first 30 minutes, then at a rate adequate to deliver the remaining dose volume over a period of 60 minutes concurrently with 125 mL normal saline. If an infusion reaction occurs during the administration of SEL-110.36, the infusion may be slowed, or stopped and then restarted at a slower rate at the discretion of the Investigator. Following the infusion of SEL-110.36, the main IV line must be flushed with normal saline prior to the start of the SEL-037 infusion. Refer to the Study Operations Manual for instructions regarding infusions for patients with medical history involving cardiovascular comorbidities.

SEL-037 infusion will start up to 30 minutes after completion of the SEL-110.36 infusion. SEL-037 will be infused via infusion pump over a time period of no less than 120 minutes. If an infusion reaction occurs during the administration of SEL-037, the infusion may be slowed, or stopped and then restarted at a slower rate at the discretion of the Investigator. Following the infusion of SEL-037, the main IV line must be flushed with normal saline.

The Investigator is permitted to modify the infusion parameters (decrease the rate of infusion or interrupt the infusion) if medically warranted in response to an AE. The Investigator will notify the unblinded medical monitor of any changes in infusion parameters. Detailed instructions for modifying the infusion parameters are included in the Study Operations Manual.

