If an infusion reaction occurs, Investigators are permitted to use concomitant medications or treatments deemed necessary to provide adequate patient care. Investigators should also utilize the infusion reaction lab kit (samples for: chemistry, hematology, coagulation, histamine, serum tryptase, and anti-uricase) provided in the Study Operations Manual to collect additional blood specimens. In the case of a Grade 3 or 4 infusion reaction occurring during an infusion, the administration of study drug should be immediately discontinued, and the affected patient should be treated according to the clinical trial site's protocol for infusion reactions (e.g., monitoring, administration of antihistamines, corticosteroids, fluids and epinephrine, as clinically indicated). The patient should be withdrawn from subsequent study drug treatment.

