An AE or suspected adverse reaction (an AE where there is a reasonable possibility that the drug caused the event; suspected drug related) is considered “unexpected” if it is not listed in the SEL-212 Investigator’s Brochure or is not listed at the specificity or severity that has been observed.

12.2.1.5 **Infusion Reactions / Adverse Events of Special Interest**

A study drug-related AE that occurs within 24 hours after initiation of study drug infusion will be assessed as an infusion reaction. An infusion reaction suspected to be anaphylaxis will be assessed according to the clinical criteria for the diagnosis of anaphylaxis based on the National Institute of Allergy and Infectious Diseases (NIAID) / Food Allergy & Anaphylaxis Network (FAAN) Symposium criteria. ([Sampson 2006](#)).

Infusion reactions will be managed and treated as described below. In addition to premedication with antihistamines and steroids ([Section 10.6.2](#)), the following steps will be implemented in this protocol to either reduce the risk of infusion reactions or manage infusion reactions.

- Patients with prior exposure to uricase therapy will be ineligible
- Patients with a history of anaphylaxis or severe allergic reactions, history of severe atopy, angioedema, or previous infusion reactions will be excluded from the trial.
- Study drug will be administered at controlled rates only in a healthcare setting and by healthcare providers sufficiently equipped and prepared to manage infusion reactions including anaphylaxis.

- In case of infusion reaction, sites will perform specific assessments as specified in the Study Operations Manual.
- Each patient will be observed for infusion reactions after dosing of study drug in the clinic for approximately 4.5 hours from the start of study drug infusion. Patients will be informed about the signs or symptoms of infusion reactions and will be instructed to notify the Investigator immediately if they believe they are experiencing a reaction.
- Each patient shall remain for a minimum of 1 hour after the completion of infusion of study drug for a period of safety observation.
- All patients will be contacted approximately 24 hours after infusion to determine whether any infusion reaction AEs occurred.
- Patients who experience an infusion reaction will be contacted approximately 24 hours after the event as follow-up.

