13.5.2 Adverse Events / Adverse Drug Reactions

All AEs will be coded and grouped into Preferred Terms (PT) by System Organ Class (SOC), using the most recent MedDRA Version. All AEs will be summarized by SOC and PT.

Summaries by each treatment group will be provided on the Safety Set overall and by SOC and PT with the number and percentage of patients reporting TEAEs, serious TEAEs, treatment-related TEAEs, AEs of special interest (AESIs), infusion reactions (this is a study drug-related AE that occurs within 24 hours after initiation of study drug infusion), TEAEs leading to withdrawal and TEAEs leading to death.

Additional analysis will be performed on a subset of infusion reactions (this is a study drug-related AE that occurs within 1 hour after completion of study drug infusion) that fulfil the criteria of an Allergic Reaction/Hypersensitivity according to the Rheumatology Common Toxicity Criteria, version 2.0. In the overall summary, additionally, the number and percentage of patients with at least one severe TEAE, with at least one moderate TEAE but no severe TEAE and with only mild TEAEs will be provided.

The number and percentage of patients with TEAEs / serious TEAEs treatment-related TEAEs / TEAEs of special interest and TEAEs leading to withdrawal will be summarized by SOC and PT for each treatment group and overall on the Safety Set.

Event rates by treatment group and overall will be provided for patients with at least one related TEAE, at least one SAE, and at least one TEAE of special interest. Additionally, the relative risk with 95% confidence interval comparing each SEL-212 treatment group to placebo as well as comparing the integrated SEL-212 arms to placebo will be provided.

TEAEs will also be summarized by maximum intensity and relationship to study drug.

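### The hypersensitivity subset of infusion reactions is timed from completion of the infusion, so as written it leaves out reactions that start during the infusion or terminate it

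*SAP*

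**What the plan says.** Two clocks are used for infusion reactions.

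- **Parent set.** Protocol 12.2.1.5 states: "A study drug-related AE that occurs within 24 hours after initiation of study drug infusion will be assessed as an infusion reaction". SAP 10.3 uses the same rule for its overall summary: "infusion reactions (this is a study drug-related AE that occurs within 24 hours after initiation of study drug infusion".
- **Hypersensitivity subset.** In the same paragraph SAP 10.3 adds an analysis of "a subset of infusion reactions (this is a study drug-related AE that occurs within 1 hour after completion of study drug infusion", restricted to events that meet the RCTC v2.0 Allergic Reaction/Hypersensitivity criteria. Protocol 13.5.2 gives the same timing: "this is a study drug-related AE that occurs within 1 hour after completion of study drug infusion".

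The protocol foresees reactions during dosing. Protocol 10.7 lets the investigator slow the infusion of either component, or stop and restart it, if a reaction occurs. It also states: "In the case of a Grade 3 or 4 infusion reaction occurring during an infusion, the administration of study drug should be immediately discontinued", and such a patient is to be withdrawn from later study drug. Protocol 12.2.2.5 codes a terminated infusion separately from a completed dose.

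Neither document says that reactions during the infusion belong to the subset. Neither says what completion means when an infusion is stopped.

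**The concern.** A programmer who follows the sentence would select events with onset between the end of the infusion and one hour later. An allergic reaction that begins while the drug is running would fail that test. So would one severe enough to end the infusion. A patient whose only qualifying event was a Grade 3 or 4 allergic reaction that stopped dosing would be counted in this analysis as having had none. Because that patient receives no further study drug, no later infusion could bring the patient into the subset.

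The rate matters for this product. Protocol 5.5 describes infusion reactions in about 26% and anaphylaxis in 6.5% of patients on the approved uricase. Protocol 7.7 lists a lower infusion-reaction risk among the advantages of SEL-212. Protocol 7.6.3.2.2 reports two SEL-212 patients with life-threatening anaphylactic reactions. With about 47 patients per arm, each patient moves an arm's rate by 1/47 = 2.1 percentage points, so even one or two misclassified patients would show.

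**Working it through.** **Inputs.** The durations are from Protocol 10.7.

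- Component 1 (SEL-110.36), first part: "infused at a rate of 1.5 mL/hr for the first 30 minutes", that is 0.5 h.
- Component 1, second part: "remaining dose volume over a period of 60 minutes concurrently with 125 mL normal saline", that is 1.0 h.
- Gap: "SEL-037 infusion will start up to 30 minutes after completion of the SEL-110.36 infusion", that is 0 to 0.5 h.
- Component 2 (SEL-037): at least 2.0 h.
- Stay after the infusion: at least 1 h (Protocol 12.2.1.5).

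**Step 1: reproduce the plan's own timeline.** End of infusion = 0.5 + 1.0 + gap + 2.0.

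- No gap: 3.5 h, and one hour later 4.5 h.
- Gap of 0.5 h: 4.0 h, and one hour later 5.0 h.

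Protocol 12.2.1.5 gives about 4.5 h of clinic observation from the start, and Appendix B marks about 3.5 h and 4.5 h. Both agree with the no-gap result. The durations are minima: a slowed or interrupted infusion is longer, and the excluded stretch grows with it.

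**Step 2: compare the windows, in hours from initiation.**

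| Window | No gap | 0.5 h gap |
|---|---|---|
| Parent set | 0 to 24 | 0 to 24 |
| Subset, literal | 3.5 to 4.5 | 4.0 to 5.0 |
| Start of infusion to 1 h after its end | 0 to 4.5 | 0 to 5.0 |
| Part of the last row outside the literal subset | 3.5/4.5 = 78% | 4.0/5.0 = 80% |
| Part inside | 1.0/4.5 = 22% | 1.0/5.0 = 20% |

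None of the infusion time lies inside the literal window.

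**Step 3: a terminated infusion.** There are two ways to program it. If no completion time exists, the event has no window and cannot qualify. If the stop time stands in for completion, the reaction that caused the stop began before it and still falls outside.

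**Step 4: can the omission be turned into a count?** No. That would need the distribution of onset times, or at least the proportion of reactions that begin during infusion. Neither document gives it.

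**The case against.** **The subset may inherit its lower bound.** It is introduced as part of a parent set that starts at initiation, so the one-hour limit could be meant only as an earlier upper cut-off. That would match the minimum one-hour stay and make the subset the on-site reactions. Since the protocol expects reactions during infusion, an intent to exclude them is implausible. This is probably what was meant, and it stands as a guess about intent. The text does not say it: the same paragraph names initiation for one clock and completion for the other. If it was the intent, the correction changes nothing that was planned.

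**Completion could be read per component.** Appendix B labels each component as a study drug infusion. Component 1 ends at 1.5 h, so its window would run to 2.5 h and take in the first 1.0 h of SEL-037 (no gap) or the first 0.5 h (0.5 h gap), including reactions there that terminate SEL-037. This would still leave out 1.5 + 1.0 = 2.5 h to 1.5 + 1.5 = 3.0 h of infusion. It is also the less natural reading, because Protocol 12.2.1.5 uses completion for the end of dosing.

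**The events are reported elsewhere.** This stands, and it limits the point. A reader might infer that these reactions vanish from the safety report, or that the plan has no other view of allergic infusion reactions. The documents do not support that. All drug-related events within 24 hours of initiation are in the infusion-reaction summary. Infusion-related reactions including anaphylaxis are of special interest, with tables by preferred term and exposure-adjusted rates. Serious events and events leading to study drug withdrawal have their own tables, and suspected anaphylaxis is assessed by separate clinical criteria. What none of these does is select events by the RCTC hypersensitivity criteria.

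**Conclusion.** The definition is wrong as written; this is more than missing detail. Followed literally, the hypersensitivity subset omits onsets during an infusion of at least 3.5 h (4.0 h with the permitted gap) and reactions that terminate it. The resulting rate would be understated and out of line with the parent set. The damage is confined to one additional, descriptive safety analysis.

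Three stronger conclusions might be drawn and should not be:

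- That all severe reactions are lost. A severe reaction starting in the hour after completion is captured; those lost are the ones that start during the infusion, including those that stop it.
- That 78% to 80% of reactions are lost. Those figures are shares of time, and the size of the undercount is unknown.
- That nearly all lost events would be in the SEL-212 arms. No figure in the documents supports it, and under blinding a placebo patient's event can also be judged drug-related.

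The conclusion rests on reading completion as the end of dosing and on the infusion times in Protocol 10.7.

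**What to change.** In SAP 10.3, define the subset as study drug-related AEs that meet the RCTC v2.0 criteria and have onset from the start of the Component 1 infusion to 1 hour after the end of the last component infused, where the end is either completion or permanent stop. Record the change in SAP section 12, before database lock. Align Protocol 13.5.2 at the next amendment; Protocol 15.3 requires investigator signature and ethics approval for amendments, so a separate one for this sentence is not warranted. The existing rule that a gout flare within 24 hours is listed as a flare, not as an infusion reaction, can stay.

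No new data are needed. Protocol 9.3 already records start and stop times of administration, and Protocol 12.2.2 requires event times while the patient is in the clinic. The cost is one sentence and its programming. The downside for the sponsor is that the reported hypersensitivity rate may be higher.

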Additional secondary efficacy endpoints will be summarized by treatment group using descriptive statistics for the ITT population and will be compared between each SEL-212 treatment group and placebo using MH or Chi-square tests, as appropriate, in case of binary endpoints or using ANCOVA or MMRM, as appropriate, in case of continuous or numerical endpoints. Exploratory p-values of two-sided tests with 95% confidence intervals for treatment differences between each SEL-212 treatment group and placebo will be presented.

Safety Analyses

All AEs will be coded and grouped into Preferred Terms (PT) by System Organ Class (SOC), using the most recent MedDRA Version. All AEs will be summarized by SOC and PT. An overall summary will be provided with the number and percentage of patients reporting TEAEs, serious TEAEs, treatment-related TEAEs, TEAEs leading to withdrawal and TEAEs leading to death. The number and percentage of patients with TEAEs /serious TEAEs / TEAEs leading to withdrawal / treatment-related TEAEs and TEAEs of special interest will be summarized by SOC and PT for each treatment group, and overall. TEAEs will also be summarized by maximum intensity and relationship to study drug. Event rates by treatment group and overall will be provided for patients with at least one related TEAE, at least one SAE, and at least one TEAE of special interest. Additionally, the rate difference with 95% confidence interval comparing each SEL-212 treatment group to placebo as well as comparing the integrated SEL-212 arms to placebo will be provided.

Laboratory data will be summarized by the type of laboratory test and will be presented for each scheduled visit stratified by treatment group and overall. Shift tables of the number of patients with low/normal/high (or abnormal/normal) values at each scheduled post-baseline visit compared to the low/normal/high (or abnormal/normal) categorization at Baseline will be provided by treatment group, and overall. Summary tables of actual values and changes from baseline will be provided for each continuous laboratory parameter at each scheduled visit by treatment group and overall.

Summary tables of the actual values and changes from baseline will be provided for each vital sign parameter at each scheduled visit by treatment group, and overall.

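### SAP 10.3 does not state the adverse event rate difference for each SEL-212 dose versus placebo, which the protocol promises, and SAP Section 12 declares no change

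*SAP*

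**What the plan says.** **SAP 10.3.** Exposure-adjusted rates are planned per arm, for overall SEL-212 and in total. They cover related TEAEs, SAEs, AESIs and specific AESIs. There are two versions:

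- patient-based: "Number of all patients with at least one event in treatment group A / Total sum of the treatment exposure time of all patients";
- event-based: "Number of all events in treatment group A / Total sum of the treatment exposure time of all patients in treatment group A".

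Contrasts are planned for a narrower list: SAEs and AESIs in at least 2% of "individuals, as well as the most common TEAEs". For these, "the rate difference of exposure-adjusted event rates between the two treatment groups together with the 95% confidence interval will be provided", and "this will also be presented for the two treatment groups combined vs. placebo".

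**Protocol synopsis, Safety Analyses.** "Event rates by treatment group and overall will be provided for patients with at least one related TEAE, at least one SAE", and likewise for AESIs. The next sentence promises "the rate difference with 95% confidence interval comparing each SEL-212 treatment group to placebo", and also the integrated SEL-212 arms against placebo.

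**Protocol 13.5.2.** The same event categories and the same two comparisons, but with a different measure: "the relative risk with 95% confidence interval comparing each SEL-212 treatment group to placebo".

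**Declared changes.** Protocol Section 13 says that modifications to planned analyses will be identified in the final SAP. SAP Section 12 lists one: ANOVA in place of ANCOVA for gout flares.

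**The concern.** The two SEL-212 arms differ only in the SEL-110.36 (rapamycin) component (Protocol 7.1.2). A central safety question is therefore whether an excess over placebo belongs to one dose or to both. Pooled SEL-212 versus placebo averages over that question, and A versus B has no placebo reference. Only each dose against placebo answers it directly, and a programmer who follows SAP 10.3 to the letter would not produce it.

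Two smaller gaps sit beside this. The protocol attaches its contrasts to patients with at least one related TEAE, and the SAP gives that category no contrast. The exposure time in both rate denominators is not defined, while TEAEs are counted to 30 days after the last dose.

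**Working it through.** The documents give no figure for these contrasts, so there is none to reproduce. The check is a comparison of the texts followed by an illustration.

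**1. Contrasts side by side**

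| Item | Protocol synopsis | Protocol 13.5.2 | SAP 10.3 |
|---|---|---|---|
| Each dose vs placebo | yes | yes | not stated |
| Pooled SEL-212 vs placebo | yes | yes | yes |
| A vs B | no | no | yes, if read literally |
| Measure | rate difference | relative risk | difference of exposure-adjusted rates |
| Contrast for related TEAEs | yes | yes | no (rate only) |

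The literal reading rests on the second SAP clause. If two groups can be combined and set against placebo, they are the two SEL-212 doses, so a difference between them is A versus B.

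**2. What the literal plan would show**

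Inputs: 47 patients per arm (SAP 3.4) and 168 days of treatment (SAP 3.3). Event counts and full exposure are assumptions.

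- Person-time per arm: T = 47 × 168 / 365.25 = 21.62 patient-years; pooled SEL-212, 43.24.
- Difference: d1/T1 − d0/T0, with SE = √(d1/T1² + d0/T0²) and 95% CI = difference ± 1.96 SE.

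Worked case, 2/2/9 events on placebo/A/B:

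- Pooled − placebo: 11/43.24 − 2/21.62 = 0.162, SE 0.101.
- B − placebo: 9/21.62 − 2/21.62 = 0.324, SE 0.153.

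| Events (placebo/A/B) | Pooled − placebo | B − A | B − placebo (unstated) | A − placebo (unstated) |
|---|---|---|---|---|
| 2/2/9 | 0.16 (-0.04 to 0.36) | 0.32 (0.02 to 0.62) | 0.32 (0.02 to 0.62) | 0.00 (-0.18 to 0.18) |
| 2/6/10 | 0.28 (0.06 to 0.50) | 0.19 (-0.18 to 0.55) | 0.37 (0.06 to 0.68) | 0.19 (-0.07 to 0.44) |

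Values are per patient-year. In the first row the pooled estimate is half the B excess and its interval includes zero. In the second row the two literal contrasts show an excess for SEL-212 as a whole and no clear dose difference. Neither shows that the interval against placebo excludes zero for B and includes it for A.

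**3. Undefined exposure time**

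For a patient given all six doses on schedule, three definitions are plausible:

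- first to last infusion: 5 × 28 = 140 days;
- 28 days per dose: 6 × 28 = 168 days;
- TEAE window: 140 + 30 = 170 days.

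The first gives rates 168/140 = 1.20 times those of the second. For a patient who stops after one dose, the three give about 0, 28 and 30 days.

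**The case against.** The strongest reply is that SAP 10.3 is a drafting slip. Its second clause begins with an also, and each dose against placebo followed by both combined against placebo is exactly the protocol's pair. No other adverse event text names an A versus B comparison. This is plausible, and a reader should not infer that the sponsor chose to replace the placebo contrast. What stands is that the sentence does not state the promised contrast under either reading.

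A reader might also infer that no dose-specific safety interval exists at all. That goes too far. The protocol's own plan remains, and per-arm counts and rates are tabulated, so the interval could be derived from planned output. Gout flare, one of the AESIs, does have each-dose-versus-placebo intervals as an efficacy endpoint on the ITT set (SAP 9.3.2.8, 9.3.2.9 and 9.3.3). The other AESIs and the SAEs do not.

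The illustration is also limited. Its counts are assumed. In the 2/2/9 case, B versus A would raise the flag. The Wald interval for 9 versus 2 events is fragile: the exact conditional test gives p = 2 × (1 + 11 + 55)/2048 = 0.065.

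Finally, it is tempting to call the patient-based rate wrong because it keeps time after the first event in the denominator. The documents do not support that. The SAP defines the rate openly, never calls it a first-event rate, and plans the event-based rate beside it. A first-event rate is a different estimand. With constant hazard over 168 days, the SAP rate is 0.109 against 0.112 per patient-year if 5% have the event, and 0.652 against 0.775 if 30% do. The choice therefore matters little for single, less common events.

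Nor does a first-event rate cure distortion from early stopping, given that the protocol describes TEAEs as most frequent after the first cycle (7.6.3.2.2). As an illustration, assume equal hazards in both arms, 40% risk over 170 days on full dosing, SEL-212 stopping of 20%, 10% and 10% after one, two and three doses, exposure of 28 days per dose in the SAP rate, and a cycle-1 hazard 3 or 5 times later cycles. The false excess on SEL-212 is then 0.118 or 0.168 per patient-year with the SAP rate, and 0.118 or 0.191 with the first-event rate.

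**Conclusion.** The point holds as an undeclared mismatch between SAP and protocol. SAP 10.3 does not state the adverse event contrast of each SEL-212 dose with placebo, and it drops the contrast for related TEAEs. The two protocol sections disagree on the effect measure, exposure time is undefined, and SAP Section 12 is silent on all of it. That the contrast is not stated is certain from the text; that A versus B was intended is not.

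The practical size is moderate. These are descriptive outputs with no decision rule and no bearing on type I error. At stake is whether a reader of the report can see which dose carries an excess over placebo. In the illustration a B-only excess of 0.32 per patient-year appears as 0.16 in the pooled contrast. That figure rests on assumed counts, 47 per arm, full 168-day exposure and Wald intervals. The SAP should be corrected, but the trial's conclusions on efficacy do not depend on it.

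**What to change.** - In SAP 10.3, name the contrasts as SEL-212A versus placebo, SEL-212B versus placebo and pooled SEL-212 versus placebo, each with a 95% CI.
- Add patients with at least one related TEAE to the categories that receive these contrasts.
- Use one effect measure in the protocol synopsis, Protocol 13.5.2 and SAP 10.3.
- Define treatment exposure time so that it matches the TEAE window in SAP 10.3, from first dose to 30 days after the last dose.
- List any intended departure from the protocol in SAP Section 12.

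Optional: for common composites such as any AESI, add a first-event rate with person-time cut at the first event, labelled as a separate estimand. It would not remove the false excess that front-loaded events and unequal follow-up can produce.

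The cost is SAP wording and modest programming, with no new data.
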